Payment occurs in the form of a check to be mailed to the study participant or electronic funds transfer within 6 to 8 weeks of completion of each study period. Participants not completing the entire study will not be compensated for incomplete study periods. The study participant's name, SSN and address will be provided on the Subject Payment Form, in addition to information regarding the amount of compensation and study information. Table 2 below outlines the Study Timeline, Table 3 outlines the assessment measures employed and timing thereof, and Table 4 outlines the contacts with study participants, the purpose of each contact, and the time commitment required on the part of participants. These timelines are considered to represent the study design and schedule we hope to achieve. However, in some cases we may be unable to contact Veterans in strict accordance with this schedule. Study participants who are non-responsive to study staff such that the timing of their involvement varies considerably from other study participants would be withdrawn from the study. In addition to the contacts outlined in Table 4, participants may also receive phone calls to remind them to complete their daily sleep diary. This is discussed in greater detail below.

C.7 Study Timeline: The study timeline is summarized in Table 2.

Study Activity (Months)	Yr 1				Yr 2				Yr 3				Yr 4	
	1	2	3	4	1	2	3	4	1	2	3	4	1	2
Study Start-Up														
Hire and Train Staff (0-6)	●	●												
Create/ test tracking databases (0-6)	●	●												
Study Conduct														
Aims 1 & 2: Recruitment (6-30)			●	●	●	●	●	●	●	●				
Aims 1 & 2: Intervention (7-32)			●	●	●	●	●	●	●	●	●	●		
Aims 1 & 2: 8 Week Follow-Up (8-33)			●	●	●	●	●	●	●	●	●	●		
Aims 1 & 2: 6 Month Follow-Up (12-37)					●	●	●	●	●	●	●	●	●	●
Aim 3: Recruitment and Qualitative Data Collection											●	●	●	●
Evaluation & Dissemination														
Aims 1 & 2 & 3 Analyses (35-40)												●	●	●

C.8 Measures

Screening Measures: The following screening measures will be used to assess eligibility.

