Substance Use/Abuse: We will define alcohol abuse as documentation in the medical record of current alcohol abuse. Those with the two most recent AUDIT-C administrations documented in the medical record and scored as negative will be eligible for the study. The AUDIT-C⁸⁸, a well-validated 3-item screener for alcohol abuse used in VA⁸⁹ and primary care settings⁹⁰, to screen out those who are actively abusing alcohol. We will use the clinical scoring criteria for men and women respectively. We will use a single item to screen out those engaged in recreational drug use⁹¹. This item was found to be highly sensitive (100%) and moderately specific (73.5%) for detecting those with a drug use disorder and had good sensitivity (81.8%) and specificity (72.5%) for laboratory-based evaluation of drug use⁹¹.

Table 3. Assessment Measures

	Items	Timing		
		BL	8 weeks	6 months
Background-EHR Data				
VA Sleep & Psychotropic Medications	n/a	•		
Medical Conditions	n/a	•		
Mental Health Conditions	n/a	•		
Background-Self Report				
Demographic Characteristics	18	•		
Medical Conditions	up to 16	•		
Primary Outcome				
Insomnia Symptom Severity: ISI	7	•	•	•
Secondary Outcomes				
Actigraphy (WASO, TST and SE)	n/a	•	•	•
Sleep Diary (SOL, WASO and SE)	8	•	•	•
Fatigue: Multidimensional Fatigue Inventory	20	•	•	•
Depression: PHQ-8	8	•	•	•
Chronotype: MEQ	19	•	•	•
Trauma-related Sleep Disturbances (PSQI Addendum)	10	•	•	•
International Physical Activity Questionnaire	11	•	•	•

Glasgow Sleep Impact Index	7	•	•	•
Insomnia Treatment Knowledge Questionnaire	10	•	•	•
Ask if participant has accessed CBTI Coach and/or Path to Better Sleep	2		•	•

Outcome Measures

Outcome measures will be collected by phone by the project's research assistant (RA) at baseline, 8 weeks, and 6 months. Copies of self-report outcome measures are listed below.

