The study coordinator will inform patients of randomization arm at the end of the baseline. The various time points have windows in which the assessment period should be completed in. Participants may start the baseline assessment up to a month after consent. The 8-week assessment can start as soon as 6 weeks after starting the intervention period (if all nurse phone calls are completed) to no later than 8 weeks after intervention period has started. Participants have a 5-week window to start and complete baseline and 8-week assessment activities. Participants have a 6-week window to begin and complete 6-month assessment activities.

Covariate and Other Measures: Due to their established association with sleep, the following variables will be evaluated as potential covariates and included in analyses as appropriate: age; gender; body mass index (BMI); co-morbid medical conditions; co-morbid mental health conditions; smoking status and pack years; anxiolytic/hypnotic usage; and other medications. Self-report information about demographic characteristics and current medical and mental health conditions will be collected at baseline. During the 8 week and 6-month Assessments, we will ask participants in the Tele-Self CBT condition if they have sought or received treatment for their sleep complaints beyond what was offered in this study.

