C.9 Missing Data: Because the main predictors of interest are collected at baseline, we do not anticipate much missing data in these variables. We do, however, anticipate some missing values in the longitudinal outcomes owing to dropout or, rarely, patients not completing the sleep diaries or returning Actiwatches. Although we did not lose any Actiwatches in our pilot study, participants did not return 2 of 162 devices (1%) in a past trial⁴. If the missing values are related to other measured patient factors, such as age, comorbidities, or employment status (as we have seen in previous studies), then multiple imputation (MI) provides a framework for incorporating information from these auxiliary variables while still preserving a parsimonious main treatment effect mode. This framework is described as a significant advantage in recommendations from the Panel on Handling Missing Data in Clinical Trials. Depending on the type and scope of missing data for other longitudinal variables, as a sensitivity analysis, MI will be conducted via the SAS procedure PROC MI or the SAS macro IVEware. A general linear model for each outcome variable will then be applied to each of the imputed datasets, and estimates combined using Rubin's rules as implemented in PROC MIANALYZE.

Table 4. Contacts with Participants

STUDY CONTACTS			
Week#	Purpose of Contact	Measures	Time Commitment/Contact Modality
0	TELEPHONE-BASED SCREENING	Shift Work Question Drug Use Screener Prior participation in CBTI Question DSISD Epworth Sleepiness Scale Insomnia Severity Index PHQ-8	30 minutes/phone call
0	CONSENT AND ENROLL		20 minutes/telephone
2	BASELINE ASSESSMENT 
 ○ Participant calls IVR sleep diary system daily for 2 weeks ○ At end of 2 weeks, participant completes baseline questionnaires by phone ○ Following questionnaire completion, participant is randomized and informed of assigned treatment arm by phone 	Adverse Events Demographic and Service Information Comorbidity Questionnaire Insomnia Severity Index (ISI) Multi-Dimensional Fatigue Inventory (MFI) Morning Eveningness Questionnaire (MEQ) Pittsburgh Sleep Quality Index (PSQI) Glasgow Insomnia Index IPAQ short phone (physical activity) Insomnia Treatment Knowledge Questionnaire Sleep Medication Question COVID questions	5 minutes daily/IVR 40-50 minutes/phone call

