3-8	INTERVENTION ARM Interventionist calls with participant to support treatment engagement and adherence.	Intervention Adherence Questions	6 nurse contacts @ 20 mins/call
3-8	HEALTH EDUCATION ARM Interventionist calls with participant to ensure equivalent contact time across arms.		6 nurse contacts @ 20 mins/call

STUDY CONTACTS			
Week#	Purpose of Contact	Measures	Time Commitment/Contact Modality
9-10	8 WEEK ASSESSMENT o Participant calls IVR sleep diary system daily for 2 weeks o At end of 2 weeks, participant completes 8-week assessment questionnaires by phone	Adverse Events query Insomnia Severity Index (ISI) Multi-Dimensional Fatigue Inventory (MFI) Morning Eveningness Questionnaire PSQI addendum Glasgow Insomnia Index IPAQ short phone Insomnia Treatment Knowledge Questionnaire PHQ-8 COVID questions Sleep medication and Other Treatment for your Sleep Complaint Intervention arm only: Treatment Acceptability/use	5 minutes daily/IVR <50 minutes/telephone
27-28	6 MONTH ASSESSMENT o Participant calls IVR sleep diary system daily for 2 weeks o At end of 2 weeks, participant completes 6-month assessment questionnaires by phone	Adverse Events query Insomnia Severity Index (ISI) Multi-Dimensional Fatigue Inventory (MFI) Morning Eveningness Questionnaire PSQI addendum Glasgow Insomnia Index IPAQ short phone Insomnia Treatment Knowledge Questionnaire PHQ-8 COVID questions Sleep medication and Other Treatment for your Sleep Complaint	5 minutes daily/IVR <50 minutes/telephone

Study Interventions

Tele-Self CBTI: The nurse interventionists will make an introductory call and set up a weekly call appointment time. As noted above, Tele-Self CBTI is comprised of two treatment components: 1) Self-management via our workbook entitled, “Improve your Sleep: A Self-Guided Approach for Veterans with Insomnia” with Session Guides; and 2) telephone-based nurse support. Our Tele-Self CBTI workbook includes the following typical CBTI treatment components: Sleep Restriction; Stimulus Control; Cognitive Therapy; Relaxation; and Sleep Hygiene Education⁹³. We will deliver Tele-Self CBTI across 6 weekly telephone contacts of 20 minutes or less. Table 5 describes the treatment modules and content of each telephone session, and the relative timing of treatment components.

Table 5. CBTI Treatment Components and Sessions

Module: Content	Veteran Workbook Readings	Nurse Support	Sleep Diary
Weekly		Weekly	Daily
1: Sleep Education; Sleep Diary Instructions	Session 1 (page 5)	X	X

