E.1 Data Summary (Aims 1 & 2): Descriptive statistics, including graphical displays, will be used to summarize all study variables, both overall and by intervention group. Evidence of imbalance in baseline characteristics will be noted and discussed as to whether they are clinically significant. As recommended by Committee for Proprietary Medicinal Products¹⁰⁸ guidelines, we will consider sensitivity analyses adjusting for these baseline characteristics to ensure that an observed intervention effect is not due to baseline imbalance. Trajectory plots and frequency distributions will be used to explore longitudinal outcomes. We do not anticipate substantial deviations from symmetric, normal distributions for the study outcome variables. Additionally, correlation patterns over time, both overall and by intervention group, will be examined via scatter plots. The main conclusions drawn from this trial will be based on the pre-specified primary and secondary hypotheses outlined below and will be tested with two-sided p-values at the standard 0.05 level. All statistical analyses will be performed using the SAS software package (Cary, NC); the Durham HSR&D Center of Innovation maintains the current SAS release on the Durham VA hospital servers.

E.2 Intent to Treat Analyses (Aims 1 & 2): All primary and secondary analyses focus on the effect of the intervention compared to control. We, therefore, plan to use the intent-to-treat assumption for all analyses; participants will be analyzed as part of the group to which they are randomized, regardless of intervention adherence.

Hypothesis 1: Relative to Health Education, participants randomized to receive Tele-Self CBT will have greater improvements in insomnia severity, as measured by the Insomnia Severity Index (ISI), at 8 weeks. The ISI is a continuous measure wherein lower scores indicate less severe insomnia symptoms. A general linear model will be used to estimate changes in ISI over time and test the primary hypothesis. Because of the small number of time points, we will apply

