E.3 Sample Size Considerations (Aims 1 & 2): Our sample size estimates are based on the Hypothesis 1 primary outcome – Insomnia Severity Index. Because this is a longitudinal study with repeated measurements on each subject, mean change is estimated with increased precision. In sample size calculations, the increase in precision can take into account the correlation between repeated measures. With Tele-Self CBT1, we anticipate seeing smaller effects than might be seen with in-person CBT1. Additionally, our comparison group receives more than usual care, again leading to smaller effects. In a recent meta-analysis, the effect of CBT1 on ISI yielded large Hedge's g effect sizes of 0.98. Conservatively, we then base our sample size estimates on an effect size of 0.5; this translates into a relative mean improvement on the ISI of at least 2.8. Assuming a baseline SD of 5.8, a repeated-measures correlation of 0.6 (both quantities estimated from previous studies^[37,52,54,114]), and a type-I error of 5%, we will need to have 73 patients in each arm to detect a relative mean improvement of 3 on the ISI with 90% power. To account for dropout and possible deviations from our assumptions, we plan to enroll and randomize 100 patients in each arm (total sample size n=200). With this sample size, we will also have adequate power to examine our secondary outcomes. For example, previous studies of SE show a baseline SD of 12.5 and repeated-measures correlation of 0.7. With our projected sample size, we will have 90% power to detect a relative improvement in SE of at least 6.2. The repeated-measures design option in PASS¹¹⁵ was used for all calculations.

E.4 Data Analysis (Aim 3)

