Patients with greater than minimal risk as assessed by the P4 will be excluded from the study, but not dropped from study participation if already enrolled, and offered a warm hand off to the VA Crisis Line in accordance with the approach suggested by the VA Crisis Line (see VA Veterans Experience website-document entitled Veteran In Crisis Handout.pdf). If they decline the warm hand off to the crisis line, the participant will be informed that a study clinician may contact him/her to talk more about his/her suicidal ideation. The study coordinator will obtain current contact information for the participant and inform [name] or [name], study clinicians who are trained in suicide assessment, who will contact the participant as necessary to ensure participant safety.

At their professional discretion, Drs. [name] or [name] will contact and assess the patient over the phone and take appropriate action. Assessment will include evaluation of suicidal plan, intent, means, history of suicidal behavior, and other relevant clinical information. If the patient is deemed to be at moderate to high risk of suicide, Drs. [name] or [name] will provide education to the patient regarding resources at VA and in the community for psychiatric emergency care. Patients will be urged to seek acute mental health care, and where possible, Drs. [name] or [name] will help establish a follow-up plan for this care.

If the patient is deemed to be at imminent risk for suicide, he/she will be asked to come to his/her local ER or VA ED immediately. If he/she is unwilling or unable to go to the nearest ER or ED, Drs. [name] or [name] will follow DVAMC policy for contacting local authorities for assistance in securing and transporting the patient to a hospital/mental health facility where he/she will receive appropriate help. When possible, Drs. [name] or [name] will remain in contact with the patient until local authorities have secured the patient. Following the contact, Drs. [name] or [name] will document the incident in CPRS and will notify via CPRS the patient's VA primary care physician and/or mental health provider.

F.4 Withdrawal of Participants

Veterans self-reporting current suicidal ideation at any time during the study protocol (both screening and study procedures) may be excluded/withdrawn from the study if the Principal Investigator deems that their continued involvement in the study could adversely impact the patient.

F.5 Data and Safety Monitoring

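### Section C.6 withdraws non-responsive participants with no threshold and no limit to the period before randomisation, and nothing says their 8-week ISI is still attempted

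*Combined protocol and SAP*

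**What the plan says.** C.6 (Participant Compensation) introduces the timeline and contact tables, calls them the schedule the team hopes to achieve, and accepts that some contacts will depart from it. It then says that anyone "non-responsive to study staff such that the timing of their involvement varies considerably from other study participants would be withdrawn from the study". It gives no number of days, missed calls or contact attempts.

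C.5 randomises after the baseline assessment, so the nurse calls and both follow-up assessments in Table 4 come after randomisation.

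C.8 gives numeric windows. The 8-week assessment may start six weeks after the intervention begins if all nurse calls are complete, and must start by eight weeks. "Participants have a 5-week window to start and complete baseline and 8-week assessment activities". C.8 states no consequence for missing a window.

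There are two kinds of call. In Table 4, weeks 3-8 of the intervention arm are described as "Interventionist calls with participant to support treatment engagement and adherence", and the control arm has a matching set. Outcomes are separate: "Outcome measures will be collected by phone by the project's research assistant (RA) at baseline, 8 weeks, and 6 months".

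E.2 says "participants will be analyzed as part of the group to which they are randomized, regardless of intervention adherence". C.9 offers multiple imputation as a sensitivity analysis, introduced by "If the missing values are related to other measured patient factors, such as age, comorbidities, or employment status". E.3 says "To account for dropout and possible deviations from our assumptions, we plan to enroll and randomize 100 patients in each arm". F.4, the section on withdrawal, deals only with suicidal ideation.

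**The concern.** Withdrawal from the study, with nothing said about continued follow-up, is most naturally read as the end of data collection. For a randomised participant withdrawn before the 8-week call, the primary outcome is then missing because of a staff decision, even if the participant could have been reached for a seven-item telephone scale. People who stop answering may differ in outcome from those who continue, and may do so differently by arm.

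Three features of the plan might be thought to cover this, and none does:

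- The intent-to-treat statement fixes the group in which a participant is analysed. It does not require that an outcome be collected.
- The mixed model and the conditional multiple imputation both rely on data being missing at random. The imputation list is illustrative and could include engagement, but modelling is a weaker substitute for a score that could have been obtained.
- The increase from 73 to 100 per arm protects precision. It does nothing about loss related to outcome.

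Without a threshold, staff may also apply the rule differently from one participant to the next.

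**Working it through.** **1. The plan's own figure.** E.3 gives SD 5.8, correlation 0.6, two-sided 5% and 90% power. The change-score SD is 5.8 × √(2 × (1 − 0.6)) = 5.188. Then n = 2 × (1.960 + 1.282)² × 5.188² / d². With d = 2.8 this is 72.1, so 73 per arm, as stated. With d = 3 it is 62.8, so 63. E.3 mentions both differences, and 73 matches 2.8. The implied allowance for loss is (100 − 73)/100 = 27%.

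**2. Precision.** The baseline-adjusted standard error of the 8-week difference is 5.8 × √(1 − 0.6²) × √(1/n₁ + 1/n₂).

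- 100 and 100: 0.656 (95% CI half-width 1.29)
- 85 and 85: 0.712
- 73 and 73: 0.768

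Losing 15% in both arms costs little and lies inside the 27% allowance. Power is not the issue.

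**3. Selection.** The documents give no withdrawal rate, so every input here except the 3-point effect is an assumption. Let

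- w = share withdrawn under the rule (5-15%)
- r = share of those who could have been reached had the rule not been applied (25-50%)
- b = share of a 3-point benefit that withdrawn Tele-Self participants obtain (0 or 0.5)
- h = how many points worse withdrawn control participants are than control participants who stay

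Among participants observed without the rule, those it would have removed form a share s = wr / ((1 − w) + wr). Estimated benefit with the rule, minus benefit without it, is s × [3(1 − b) − h]. When h = 0, loss in the control arm is unrelated to outcome. When h > 0, the same w and r are taken in both arms.

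| w | r | s | b | h | Gap (ISI points) | Gap / 0.656 |
|---|---|---|---|---|---|---|
| 0.05 | 0.25 | 0.013 | 0.5 | 0 | +0.019 | 0.03 |
| 0.15 | 0.50 | 0.081 | 0.5 | 0 | +0.122 | 0.19 |
| 0.10 | 0.50 | 0.053 | 0 | 0 | +0.158 | 0.24 |
| 0.15 | 0.50 | 0.081 | 0 | 0 | +0.243 | 0.37 |
| any | any | – | 0.5 | 1.5 | 0 | 0 |
| 0.05 | 0.25 | 0.013 | 0.5 | 3 | −0.019 | −0.03 |
| 0.15 | 0.50 | 0.081 | 0.5 | 3 | −0.122 | −0.19 |

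Positive means the benefit is overstated because of the rule; negative means it is understated.

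In the +0.243 row, the benefit under full follow-up would be 3 × 0.85 = 2.55. The total overstatement is therefore 0.45, and 0.45 − 0.24 = 0.21 comes from people no rule could have reached. A simulation of 8,000 trials for that row, with a baseline-adjusted model on the observed 8-week values, gave 3.01 with the rule, 2.76 without it and 2.56 with full follow-up, in line with the formula.

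**4. Windows.** On the C.8 figures the 8-week assessment closes between 6 + 5 = 11 and 8 + 5 = 13 weeks after the intervention starts, depending on how the two statements are combined. A numeric reference for timing therefore exists, and C.6 does not use it.

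**The case against.** The rule is narrower than it first looks. It needs both non-response and a resulting considerable departure in timing, and it follows a sentence that tolerates departures from schedule. Many people who do not answer staff could not give a telephone ISI under any rule. All of this stands, and it limits the likely size.

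A reader might infer that missing nurse calls is enough to be withdrawn before the outcome call is tried, since the wording refers only to study staff and covers both kinds of call. C.8 points the other way. Complete nurse calls are a condition only for the early start at six weeks, and the assessment is still to begin by week eight. Payment in C.6 is also tied to assessments and diaries, not to nurse calls. Withdrawal for missed nurse calls alone is possible under the wording but not clearly intended.

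A reader might infer a bias in favour of Tele-Self. The documents do not support a direction. Both arms get six nurse contacts of the same planned length, nothing suggests different withdrawal rates, and equal withdrawal can give no bias or an understated effect.

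A reader might infer a breach of intent-to-treat, or a contradiction with F.3, where patients above minimal suicide risk are excluded at screening "but not dropped from study participation if already enrolled". Neither holds. Analysis by randomised group is untouched, and F.3 concerns suicide risk, not administrative non-response.

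Finally, pursuing outcomes could produce late values, and counting those as the 8-week result would blur the line that C.1 draws between immediate and sustained effects. That objection is sound, and the fix keeps late values out of the primary analysis.

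**Conclusion.** The gap holds on the text: no threshold, no restriction to the pre-randomisation period, no link to the C.8 windows, and no statement that the primary outcome is still attempted. Following the rule as written can create avoidable missing primary outcomes that may be related to outcome.

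Its frequency, and the size and direction of any bias, cannot be determined from the documents. The illustrations run from about 0.24 points overstated (0.37 standard errors) to about 0.12 points understated, with zero between. These depend wholly on the assumed withdrawal, benefit and reachability values and are not bounds. Precision is adequately protected. This is a cheap improvement, not a threat to the trial's validity, and staff may in practice keep calling; the protocol should say so.

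**What to change.** Replace the C.6 sentence with wording such as:

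> After randomisation, non-response does not by itself end outcome follow-up. The 8-week and 6-month ISI are attempted within the C.8 assessment windows for every randomised participant who has not withdrawn consent, regardless of nurse-call attendance; F.4 applies unchanged.

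If a non-response withdrawal rule is kept, confine it to the period before randomisation and tie it to the C.8 baseline windows. Record any ISI obtained after its window with its actual date, and use it only in a sensitivity analysis, not as the primary 8-week value. The change concerns outcome collection only.

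The cost is a short protocol edit with a cross-reference, some extra telephone attempts by existing staff (number unknown), and one extra sensitivity run.
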